2.5.2 Statistical hypothesis, model, and method of analysis

The statistical hypothesis for ASAS 20 being tested is that there is no difference in the proportion of patients fulfilling the ASAS 20 criteria at Week 12 in the Secukinumab 300 mg treatment group versus placebo group.

Let p_0 denotes the proportion of ASAS 20 responders at Week 12 for placebo group and p_1 denotes the proportion in secukinumab 300 mg treatment group.

In statistical terms, the following hypothesis will be tested:

$H_0: p_1 = p_0$, versus $H_{A1}: p_1 \neq p_0$

In other words,

H_0 : Secukinumab 300 mg treatment group is not different to placebo group with respect to ASAS 20 response at Week 12

The primary analyses will be conducted via logistic regression with treatment and concomitant MTX intake status as factors. The Odds ratio, 95% confidence interval (CI) and p-value will be presented comparing secukinumab 300 mg treatment group to placebo group at Week 12.

[figure not shown]
The study is said to be positive/declared as success if the lower limit of 95% CI of odds ratio is greater than 1.

Summary statistics will also be reported for each treatment group, concomitant MTX intake status and by visit. Graphical representation will also be performed.

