2.6.2 Statistical hypothesis, model, and method of analysis

The statistical hypothesis for ASAS 20 being tested is that there is no difference in the proportion of patients fulfilling the ASAS 20 criteria at Week 12 in the Secukinumab 150 mg treatment group versus placebo group, after superiority is demonstrated for secukinumab 300 mg to placebo at Week 12.

Let p_0 denotes the proportion of ASAS 20 responders at Week 12 for placebo group and p_2 denotes the proportion in secukinumab 150 mg treatment group.

If primary objective (superiority of secukinumab 300mg to placebo) is met, the following hypothesis will be tested:

$H_0: p_2 = p_0$, versus $H_{A2}: p_2 \neq p_0$

In other words,

H_2 : Secukinumab 150 mg treatment group is not different to placebo group with respect to ASAS 20 response at Week 12

The key secondary analyses will be conducted analogous to the primary analyses, i.e., via logistic regression with treatment and concomitant MTX intake status as factors. The Odds ratio, 95% confidence interval (CI) and p-value will be presented comparing secukinumab 150 mg treatment group to placebo group at Week 12.

Summary statistics will also be reported for each treatment group and by visit. Graphical representation will also be performed.

[figure not shown]
Testing strategy

The family-wise error will be set to $\alpha=5\%$ (2-sided). H_1 is tested at α (2-sided). The graphical approach of Bretz ([Bretz et al 2009](#)) for sequentially rejective testing procedures is used to illustrate the hierarchical testing strategy ([Error! Reference source not found.](#)).

The following hypothesis will be tested sequentially and are included in the hierarchical testing strategy and type-I-error will be set such that a family-wise type-I-error of 5% is kept:

The testing sequence will continue to H_2 at α (2-sided) only if H_1 has been rejected.

Figure 2.6-1: Testing Strategy

Of note, in the description above, rejection of a hypothesis refers to rejection of the two-sided hypothesis; however, the level of a rejected hypothesis is only passed on according to the graphical procedure for the test of another hypothesis if the treatment effect is in favor of secukinumab.

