5.4.2 Odds ratio and 100*(1- α)% confidence interval

For an investigational drug group with n_1 subjects at risk, independent from the control group (e.g. placebo or comparator) with n_0 subjects at risk, of whom x_1 and x_0 experience a certain event with probability π_1 and π_0 respectively, the odds ratio is estimated as

$$\frac{p_1/(1-p_1)}{p_0/(1-p_0)}$$
 with $p_1=x_1/n_1$ and $p_0=x_0/n_0$. A conditional exact $100*(1-\alpha)\%$ confidence interval can be obtained by using the SAS procedure PROC FREQ with statement EXACT

OR. However, to be able to adjust for covariates odds ratios will primarily be obtained from PROC GENMOD.

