Calculate binomial proportion and standard error for each imputation.

```
proc freq data=<ASAS20>;  
by treat visit_imputation_;  
tables <response> / binomial (level=2 cl=wilson correct) ;  
ods output BinomialProp=imp_bpr;  
run;
```

Transpose the dataset for subsequent use with PROC MIANALYZE.

```
proc transpose data=imp_bpr out=imp_trs(drop=_name_) ;
by treat visit _imputation_ ;
var nvalue1; id name1; idlabel label1;
run;
```

Apply LOGIT transformation: $y = \log(p/(1-p))$ and std. err. transformation: $\text{se} = \text{se}/(p^*(1-p))$

```
data logit;
set imp_trs(rename=(_bin_=p e_bin=se));
by treat visit _imputation_ ;
lmean=log(p/(1-p));
lse=se/(p*(1-p));
run;
```

The transformed binomial proportion estimates and standard errors are combined by applying Rubin's rules for multiple imputed data sets.

```
proc mianalyze data=logit;
by treat visit ;
modeleffects lmean;
stderr lse;
ods output ParameterEstimates=logitres;
run;
```

The combined data should be transformed back using the following formula: $p = 1/(1+\exp(-y))$

```
data miexpress;
set logitres;
by treat visit ;
resti = 1/(1+exp(-estimate));
rlow = 1/(1+exp(-lclmean));
rupp = 1/(1+exp(-uclmean));
run;
```

Of note, sometimes all responses may be imputed to 0 or 1 at a given combination of response variable, treatment group and visit. Such cases should be considered separately. The combined final response rate would be the same as the original response but the 95% CI will be undefined.

The odds ratio will be derived using GENMOD for each imputation, then combined using Rubin's rules again.

```
proc genmod data = asas20_mi descending;
by avisitn_imputation_;
class trt_TNFRESN ;
model aval = trt_TNFRESN weight / link=logit dist=bin;
lsmeans trt_ / diff;
estimate 'AIN457 75mg mg vs Placebo' trt_ 1 0 -1;
estimate 'AIN457 150mg mg vs Placebo' trt_ 0 1 -1;
ods output Estimates=imp_est;
run;
```

```
proc mianalyze data=imp_est;
by avisitn trt_ ;
modeleffects LBetaEstimate;
stderr StdErr;
ods output ParameterEstimates=res;
run;
```

For sensitivity analysis, the above code will be used for non-responder imputation. In addition to that, the above analysis will also be performed for each baseline variables (e.g: sex, age class, disease severity at Baseline).

Non-parametric ANCOVA model

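### The GENMOD code that produces the pooled primary odds ratio fits a different model from the one stated in 2.5.2 and 2.6.2, and has no contrast labelled 300 mg

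*SAP*

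**What the plan says.** For the primary comparison, SAP 2.5.2 states: "The primary analyses will be conducted via logistic regression with treatment and concomitant MTX intake status as factors". The study is "declared as success if the lower limit of 95% CI of odds ratio is greater than 1". SAP 2.6.2 tests 150 mg against placebo only after 300 mg has succeeded, again "via logistic regression with treatment and concomitant MTX intake status as factors".

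Missing ASAS 20 data are multiply imputed (2.5.3, 2.6.3), so the deciding figure is a pooled odds ratio. Two places name its source. SAP 5.4.2 says that "to be able to adjust for covariates odds ratios will primarily be obtained from PROC GENMOD". SAP 5.6.1 (Primary analysis) says: "The odds ratio will be derived using GENMOD for each imputation, then combined using" Rubin's rules. The code beneath that sentence has the model line "model aval = trt_TNFRESN weight / link=logit dist=bin" and two contrasts, "estimate 'AIN457 75mg mg vs Placebo' trt_ 1 0 -1" and "estimate 'AIN457 150mg mg vs Placebo' trt_ 0 1 -1". SAP 5.6.2 reuses the code for the key secondary analysis, and 5.6.1 reuses it for the non-responder sensitivity analysis.

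**The concern.** The text and the code specify different models for the same confirmatory number. Different covariates give a different conditional odds ratio and a different confidence interval, and the success rule acts on that interval. A programmer following 5.6.1 would take the success limit from a model that 2.5.2 does not describe. The output would have no row labelled with the primary dose.

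The labels matter because the hierarchy depends on dose: 300 mg is tested first and gates 150 mg. A misread row could swap the two steps. SAP 2.1 also unblinds a selected sponsor team at the Week 12 freeze, so two candidate models should not still be open then.

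**Working it through.** **1. Text against code, term by term**

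| Item | 2.5.2, 2.6.2 and opening of 5.6.1 | GENMOD step in 5.6.1 |
|---|---|---|
| Treatment | yes | yes |
| Concomitant MTX intake status | yes | absent |
| TNFRESN | no | yes (class variable, not defined in the visible text) |
| Weight | no | yes (not in CLASS) |
| Primary contrast | 300 mg vs placebo | none labelled 300 mg |
| Key secondary contrast | 150 mg vs placebo | one labelled 150 mg |
| Other contrast | none | one labelled 75 mg, not an arm |

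The missing space between the treatment variable and TNFRESN is probably a PDF reading loss and is not counted as an error.

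**2. Could other code supply the stated model?** The PROC LOGISTIC code at the start of 5.6.1 uses TRT and STRATA. STRATA can be read as MTX status, but that code has no step by imputation and no pooling. GENMOD is the only code given for the pooled odds ratio.

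**3. What the contrasts estimate.** The SAP does not state the level order of the treatment variable. It lists the arms in two orders, both with placebo last:

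| Level order | `1 0 -1` (labelled 75 mg) | `0 1 -1` (labelled 150 mg) |
|---|---|---|
| 150, 300, placebo (Section 1.1) | 150 mg vs placebo | 300 mg vs placebo |
| 300, 150, placebo (Section 2.4.1) | 300 mg vs placebo | 150 mg vs placebo |

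The 300 mg comparison is mislabelled in both. In the first order, the row labelled 150 mg is the 300 mg result.

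**4. Signs of carry-over.** SAP 5.6.1 sets the seed as 457 followed by the study code, yet the code uses 4572310. Study 2310 is the AS trial in Section 3, which did not test 300 mg; this trial is F3302. The NParCov3 calls still stratify on TNF status, although Section 1.1 says randomization is not stratified.

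**5. The plan's own figures.** Section 3 assumes 60% (300 mg), 57% (150 mg) and 40% (placebo), with 150 per group and two-sided 5% Fisher tests. Exact enumeration gives power of 92.9% for 300 mg (stated 92%) and 82.6% for 150 mg (stated at least 80%), so both are reproduced. The implied unadjusted odds ratios are (0.60/0.40)/(0.40/0.60) = 2.25 and (0.57/0.43)/(0.40/0.60) = 1.99. The code fault changes none of these.

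**6. Size of the discrepancy.** The SAP gives no MTX prevalence and no covariate effects, so these are assumptions: MTX use 40%; MTX odds ratio 0.7, 1.0 or 1.5; weight odds ratio per SD 1.0, 0.8 or 0.6 (nine combinations); TNFRESN constant; complete data. With 150 per arm, treatment + MTX (text) and treatment + weight (code) were fitted to the same simulated trials. Success was a lower Wald 95% limit above 1. Ranges are over the nine combinations, with 8,000 trials each at planning rates and 16,000 each under the null.

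| Quantity | Text model | Code model |
|---|---|---|
| Geometric mean OR, 300 mg | 2.26 to 2.30 | 2.25 to 2.39 |
| Power, 300 mg | 93.4% to 94.3% | 93.3% to 95.0% |
| False success, 300 mg (40% in all arms) | 2.4% to 2.7% | 2.5% to 2.7% |

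At planning rates the verdicts differ in 0.7% to 2.4% of trials for 300 mg and in 1.5% to 5.0% for 150 mg tested alone. Under the null, false success for 300 mg is 2.7% to 3.2% if either model could be reported.

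**The case against.** The strongest reply is that the governing model is not in doubt. It is stated repeatedly, and the appendix code is a template. The imputation and PROC FREQ steps contain unfilled placeholders, the imputation variables run to week 16 although the text stops at Week 12, and 75 mg is not an arm. A programmer would have to rewrite the code and would use 2.5.2 to do so. Contrast labels do not change coefficients, and with placebo last both dose comparisons are computed. TNFRESN should vary little, because prior biologic exposure is a listed eligibility deviation (5.7). The practical difference then reduces to MTX versus weight, and its effect is small.

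Much of this stands. The effect is small, and a real swap of the two hypotheses cannot be shown without the level order. The 2.7% to 3.2% figure supposes a choice of model that the text does not allow. The seed, the undefined STRATA and the NParCov3 strata are secondary. One detail points the other way: with the gate of 2.6.2 applied, a smaller simulation (4,000 trials per combination) put disagreement on 150 mg at about 2% to 6%, slightly above the figure for 150 mg alone.

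The template argument does not settle the matter. The placeholders are in the imputation and PROC FREQ steps. The GENMOD model line is filled in and follows a directive sentence, and nothing in the visible text calls it illustrative or says that 2.5.2 prevails.

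**Conclusion.** The concern holds. The step that produces the success criterion omits the one covariate the SAP specifies, adds two it does not, and labels no contrast with the primary dose. The key secondary test and the non-responder sensitivity analysis inherit the fault.

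The importance lies in where the fault sits, not in the bias expected. Either model fixed in advance keeps false success close to the nominal 2.5% in the favourable direction, and the verdict would rarely change. Those sizes rest on the assumed MTX and weight effects and on complete data. The mismatch between text and code needs no assumption. It should be corrected before unblinding.

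**What to change.** In the GENMOD step of 5.6.1:

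- Fit treatment plus concomitant MTX intake status, with MTX status in CLASS, and remove TNFRESN and weight.
- Label the contrasts 300 mg vs placebo (H1) and 150 mg vs placebo (H2), and state the treatment level order the coefficients assume.
- Pool in MIANALYZE by contrast label.

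Elsewhere in the SAP:

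- Define STRATA in the PROC LOGISTIC code as concomitant MTX intake status.
- Set the seed by the SAP's own rule for this study.
- Add one sentence saying that the model in 2.5.2 prevails over the appendix code.

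Optionally, name response as the modelled event in PROC LOGISTIC, and replace or justify TNF status as the stratum in the NParCov3 calls.

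The cost is SAP wording and code only. No new data are needed, and the sample size does not change.

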1.1 Study design

This is a 52-week, randomized, double-blind, double-dummy, placebo-controlled, multicenter study to assess the efficacy of secukinumab 150 mg or 300 mg in patients with AxPsA who have had an inadequate response to two different NSAIDs. The study will consist of two treatment periods; a double-blind placebo-controlled period from Baseline to Week 12 followed by a double-blind secukinumab treatment period from Week 12 to Week 52.

The schematic of study design is given in Figure 1.1 below.

Planned number of patients and randomization

A total of 495 patients (165 patients per group) will be recruited to compensate dropouts and protocol violators.

Patient eligibility will be assessed during a maximum screening period of 8-weeks. At Baseline, all patients whose eligibility is confirmed will be randomized in a 1:1:1 ratio to secukinumab 150 mg, secukinumab 300 mg or placebo. At Week 12, patients randomized to placebo at Baseline will be re-randomized (1:1) to active treatment with secukinumab 150 mg or secukinumab 300 mg.

Group 1: secukinumab 150 mg

Treatment Period 1

secukinumab 150 mg (1 × 1.0 mL prefilled syringes (PFS)) + placebo (1 × 1.0 mL PFS) at Baseline, Week 1, 2, 3 and 4, then 4 weeks later at Week 8.

Treatment Period 2

secukinumab 150 mg (1 × 1.0 mL PFS) + placebo (1 × 1.0 mL PFS) administered every 4 weeks from Week 12 to Week 52 (last dose on Week 48).

Group 2: secukinumab 300 mg

Treatment Period 1

secukinumab 300 mg (2 × 1.0 mL PFS) administered at Baseline, Week 1, 2, 3 and 4, then 4 weeks later at Week 8.

Treatment Period 2

secukinumab 300 mg (2 × 1.0 mL PFS) administered every 4 weeks from Week 12 to Week 52 (last dose on Week 48).

Group 3: placebo

Treatment Period 1

placebo (2 × 1.0 mL PFS) administered at Baseline, Week 1, 2, 3 and 4, then 4 weeks later at Week 8.

Treatment Period 2

secukinumab 150 mg (1 × 1.0 mL PFS) + placebo (1 × 1.0 mL PFS) administered every 4 weeks from Week 12 to Week 52 (last dose on Week 48), OR

secukinumab 300 mg (2 × 1.0 mL PFS) administered every 4 weeks from Week 12 to Week 52 (last dose on Week 48).

[figure not shown]
Patients, investigator staff, persons performing the assessments and data analysts will remain blinded to the identity of the treatment from the time of randomization until database lock. No stratification at randomization will be performed.

Primary analysis time point

The primary and key secondary analyses will be performed at Week 12.

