2.2 Analysis sets

The following analysis sets will be used in this trial:

Randomized set: The randomized set will be defined as all patients, who were randomized.

Unless otherwise specified, mis-randomized patients (mis-randomized in IRT) will be excluded from the randomized set.

Mis-randomized patients are defined as those patients, who were mistakenly randomized into the IRT prior to the site confirming all eligibility criteria had been met and to whom no study medication was given. Mis-randomized patients are treated as screen failures.

Any in-eligible patient, who has been randomized and treated during the study, should be part of Randomized Set and Safety Set but excluded from FAS.

Full analysis set (FAS): The FAS will be comprised of all patients from the randomized set, to whom study treatment has been assigned. Following the intent-to-treat principle, patients will be evaluated according to the treatment assigned to at randomization.

Per-protocol set: This set includes all patients, who completed the study without a major protocol deviation.

Safety set: The safety set includes all patients, who took at least one dose of study treatment during the treatment period. Patients will be evaluated according to treatment received.

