A non-parametric ANCOVA model ([Koch 1998](#)) will be used as sensitivity analysis for ASAS 20 and possibly also for continuous endpoints that are not normally distributed. The macro NParCov3 will be used ([Zink 2012](#)).

For continuous response variable, the macro call will be as follows:

```
%NParCov3(OUTCOMES = response, COVARS = weight baseline, C = 1, HYPOTH = ALT,
STRATA = TNF $\alpha$  status, TRTGRPS = treatment, TRANSFORM = NONE, COMBINE = FIRST,
DSNIN = RESP, DSNOUT = OUTDAT);
Data set _OUTDAT_DEPTEST provides results for the treatment difference, and
_OUTDAT_CI provides a 95% confidence interval for the treatment estimate.
```

For binary response variable, the macro call will be as follows:

```
%NParCov3(OUTCOMES = response, COVARS = weight, C = 1, HYPOTH = ALT,
STRATA = TNF $\alpha$  status, TRTGRPS = treatment, TRANSFORM = LOGISTIC, COMBINE = FIRST,
DSNIN = RESP, DSNOUT = OUTDAT);
```

The odds ratio and confidence interval are to be obtained from _OUTDAT_RATIOCI.

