5.7 Rule of exclusion criteria of analysis sets

Table 5-1 Protocol deviations that cause subjects to be excluded

Deviation ID	Description of Deviation	Exclusion in Analyses	Severity code
INCL01	Informed consent not obtained before study inclusion	EXCLUDE FROM FAS AND SAF	3
INCL02	Informed consent not signed or missing or date of signing ICF is missing.	EXCLUDE FROM FAS AND SAF	3
INCL03	BASDAI score is < 4 at baseline	EXCLUDE FROM FAS	1
INCL04	Spinal Pain VAS score is < 40 at Baseline	EXCLUDE FROM FAS	1
INCL05	No inadequate response to at least 2 NSAIDs over a period of 4 weeks	EXCLUDE FROM PPS	4
INCL06	Subject <18 years of age	EXCLUDE FROM FAS AND SAF	3
INCL07	Patient has no axial PsA diagnosis at screening	EXCLUDE FROM PPS	4
INCL08	CASPAR score is < 3 at screening	EXCLUDE FROM PPS	4
INCL09	Patient is a lactating woman	INCLUDE IN EVERYTHING	0
EXCL01	Evidence of ongoing infectious or malignant processes, obtained within 3 months prior to Screening by Chest X ray or MRI	INCLUDE IN EVERYTHING	0
EXCL02	Patient takes high potency opioid analgesics	EXCLUDE FROM PPS	4
EXCL03	History of exposure to other IL-17 or IL-23 inhibitor biologic drug(s)	EXCLUDE FROM PPS	4
EXCL04	History of exposure to previous biologic DMARD(s)	EXCLUDE FROM PPS	4

Deviation ID	Description of Deviation	Exclusion in Analyses	Severity code
EXCL05	Current treatment with DMARD(s) other than MTX at baseline	EXCLUDE FROM PPS	4
EXCL06	Any therapy by intra-articular injections within 4 weeks before randomization	EXCLUDE FROM PPS	4
EXCL07	Patient taking NSAIDs is not on a stable dose for at least 2 weeks before randomization.	EXCLUDE FROM PPS	4
EXCL08	Patient taking systemic corticosteroids is not on a stable dose \leq 10 mg/day of prednisone for at least 2 weeks before randomization.	EXCLUDE FROM PPS	4
EXCL09	Patients who are on MTX (\leq 25 mg/week) who are not on a stable dose for at least 4 weeks before randomization	EXCLUDE FROM PPS	4
EXCL10	Patients on MTX who are not on folic acid supplementation at randomization	INCLUDE IN EVERYTHING	0
EXCL11	Patients who are on DMARD(s) other than MTX and who have not discontinued the DMARD(s) 4 weeks before randomization (8 weeks for leflunomide unless cholestyramine washout has been performed)	EXCLUDE FROM PPS	4
EXCL12	Active ongoing inflammatory diseases other than psoriasis that might confound the evaluation of the benefit of secukinumab therapy	EXCLUDE FROM PPS	4
EXCL13	Positive pregnancy test result before randomization	INCLUDE IN EVERYTHING	0

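### The non-parametric sensitivity analysis of ASAS 20 stratifies by an undefined TNFα status and omits MTX, so it is not a like-for-like counterpart of the primary model

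*SAP*

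**What the plan says.** Section 2.5.2 sets the primary analysis of ASAS 20 at Week 12 as "logistic regression with treatment and concomitant MTX intake status as factors". Section 5.6.1 (Primary analysis) repeats this. No other covariate appears in the text of the primary model.

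Later in section 5.6.1, under the non-parametric ANCOVA model, the SAP names an analysis that "will be used as sensitivity analysis for ASAS 20 and possibly also for continuous endpoints that are not normally distributed". Two macro calls follow, each introduced as the call that will be used. The binary call has "OUTCOMES = response, COVARS = weight, C = 1, HYPOTH = ALT", then TNFα status as the stratum argument, then "TRTGRPS = treatment, TRANSFORM = LOGISTIC, COMBINE = FIRST". The continuous call has the same stratum and takes weight and the baseline value as covariates. MTX is in neither.

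Four other places bear on this:
- Section 1.1: "No stratification at randomization will be performed".
- Table 5-1 in section 5.7: EXCL04 lists earlier exposure to biologic DMARDs as a deviation, with code 4 (out of the PPS only).
- Section 2.2: a patient who is ineligible but was randomized and treated "should be part of Randomized Set and Safety Set but excluded from FAS".
- Section 5.6.1, GENMOD code for the imputed data: the model contains a TNF variable and weight, no MTX, and a contrast for a 75 mg dose that this trial does not have.

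**The concern.** A sensitivity analysis that swaps logistic regression for a non-parametric method tells the reader most when the adjustment stays the same. Here the only adjustment factor of the primary model is removed, a different stratum is put in its place, and weight is added without a stated reason. If the two odds ratios differ, the reader cannot tell whether the method or the covariates caused it.

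The chosen stratum also has no evident role in this trial. The text of the SAP does not mention TNF status in any analysis; it appears only in code. It was not used in randomization, and the exclusion on prior biologics leaves it little or no variation if it means prior anti-TNF exposure. The neighbouring code suggests that the block was carried over from another study. The contrast is for 75 mg, and the imputation seed ends in 2310, although the stated rule uses the study code and this study is F3302. Section 3 identifies F2310 as a study in AS.

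Section 5.6.2 applies the code above it to the 150 mg comparison, so the same mismatch would reach the key secondary endpoint.

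**Working it through.** **1. Terms side by side**

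| Analysis | Stratum or factor | Covariate | MTX? |
|---|---|---|---|
| Primary model, section 2.5.2 | MTX status | none | yes |
| Non-parametric, binary call | TNFα status | weight | no |
| Stated continuous models, sections 2.7.2 and 2.11 | visit, MTX status | baseline value | yes |
| Non-parametric, continuous call | TNFα status | weight, baseline value | no |

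Both calls differ from their stated counterparts in the stratum and in weight.

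**2. The plan's own figures**

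Section 3 assumes 60% (300 mg), 57% (150 mg) and 40% (placebo), with 150 per group, two-sided 5% and Fisher's exact test. Exact enumeration gives 92.9% power for 60% against 40% (stated 92%) and 82.6% for 57% against 40% (stated at least 80%). Both agree. This point does not depend on them; the rates are reused below.

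**3. What a single-level stratum does**

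Take the stratified difference as d = Σ w_h d_h / Σ w_h, with w_h = n1_h n0_h / (n1_h + n0_h). With one stratum the weight cancels and d = d_1, the unstratified difference. One simulated data set of 165 against 165 gave 0.1152 with a constant stratum, 0.1152 with none, and 0.1184 with an MTX stratum. A constant stratum is therefore inert: it does no harm and does not stand in for MTX. The SAP does not describe the macro's own weights, so this illustrates the principle and is not a run of the macro.

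**4. How much omitting MTX could move the odds ratio**

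Without MTX: (0.60/0.40) / (0.40/0.60) = 2.25.

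With MTX, let π be the proportion on MTX, b the log odds ratio of MTX for response, and expit(x) = 1/(1 + e^(−x)). Solve for a and then t, with no interaction:
- 0.40 = π·expit(a + b) + (1 − π)·expit(a)
- 0.60 = π·expit(a + b + t) + (1 − π)·expit(a + t)

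The MTX-conditional odds ratio is e^t. The SAP gives neither π nor b, so both are assumed:

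| π | MTX OR 1.0 | 1.5 | 2.0 | 3.0 |
|---|---|---|---|---|
| 30% | 2.25 | 2.27 | 2.30 | 2.37 |
| 50% | 2.25 | 2.27 | 2.31 | 2.39 |
| 60% | 2.25 | 2.27 | 2.30 | 2.39 |

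The largest shift is 2.39/2.25 = 1.06, about 6%.

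**5. Whether a small TNF stratum can arise**

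Under section 2.2, ineligible treated patients leave the FAS, so the factor has one level. Under Tables 5-1 and 5-2, EXCL04 carries code 4, while only codes 1 and 3 remove a patient from the FAS, so such patients stay. Suppose m of them are among the 330 patients in two arms (165 + 165). For m of 2 or more, the chance that one arm of the stratum is empty is 2 × C(165, m) / C(330, m):
- m = 1: 100% (necessarily)
- m = 2: 2 × (165 × 164)/(330 × 329) = 50%
- m = 3: 25%
- m = 5: 6%

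A stratum with one arm empty holds no treatment comparison. The values of m are assumptions.

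**The case against.** The strongest reply is that this is a supportive analysis and the arms are randomized. Leaving out MTX does not bias a comparison of randomized groups, and a constant stratum drops out. That stands. A reader might infer that the analysis says nothing about the primary result, or that agreement and disagreement are both uninterpretable. The SAP does not support that: what remains is a valid weight-adjusted comparison, and the likely shift from omitting MTX is small.

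It is also fair to say that the SAP nowhere promises to vary only one element. A check that also changes the covariates is less clean, not invalid. Weight is not foreign to this SAP either: it is in the imputation model, the GENMOD code and the longitudinal mixed model.

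A reader might further take TNFα status to be exactly constant. That is an inference from EXCL04 and from reading the undefined term as prior anti-TNF exposure. Likewise, instability from a sparse stratum arises only if Table 5-1, and not section 2.2, governs the FAS.

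The code cannot be set aside as illustrative. The macro calls are introduced as those that will be run, and they name a specific variable where the PROC LOGISTIC code has only a generic stratum. Use for continuous endpoints is only a possibility in the SAP, so the loss of MTX there is conditional.

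The GENMOD code probably shares the same origin, but its correction would leave these two calls unchanged.

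**Conclusion.** The specification error is real and limited. The sensitivity analysis for ASAS 20 uses a stratum that is undefined, played no part in randomization and very probably has one level. It leaves out the one factor for which the primary model adjusts. It remains a valid comparison of randomized arms, but a difference from the primary odds ratio could not be assigned to method rather than covariates.

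The primary test, type I error and power are untouched. The effect of omitting MTX is at most about 6% on the odds ratio over the assumed ranges of MTX prevalence and effect. A tiny or one-armed TNF stratum is a possibility that depends on an unresolved conflict between section 2.2 and Table 5-1. The point should be corrected before the analysis is programmed; it does not threaten the trial's conclusion.

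**What to change.** - In both macro calls, replace TNFα status with concomitant MTX status, defined exactly as in the primary model.
- Keep the baseline value as covariate in the continuous call.
- Give a reason for weight or drop it. In the binary call it is the only covariate, so dropping it leaves a purely MTX-stratified comparison. Do not add weight to the primary model to make the two match.
- Correct the same TNF term in the GENMOD code of section 5.6.1, so that the odds ratio from the imputed data follows the stated model.
- State whether EXCL04 patients are in the FAS, so that section 2.2 and Table 5-1 agree.

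The cost is a few arguments in code, one sentence on weight and one on the FAS. Sample size and data collection do not change.
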